| Immunogenicity (C1 INH antibody) | X | | X |
| Quality of life questionnaire (AE-QoL) | X | | |
| PK/PD assessments | X ^f | | |

AE-QoL=angioedema quality of life; aPTT=activated partial thromboplastin time; BP=blood pressure; C1 INH=C1 inhibitor; INR=international normalized ratio; PD=pharmacodynamics; PK=pharmacokinetics; PT=prothrombin time; SAE=serious adverse event

- a: If a subject prematurely discontinues investigational product, regardless of the reason, the Early Discontinuation Visit procedures listed in Schedule 3 are to be performed as completely as possible. Whenever possible, all discontinued subjects should also complete the 1-Week and 1-Month Post-treatment Follow-up visits.
- b: Vital signs will be measured using standard methods at each study site.
- c: All females of childbearing potential (in accordance with standards at the site).
- d: Subjects who prematurely discontinue should complete the study diary on the day of discontinuation.
- e: Adverse events will be collected through 7 days after the last dose of investigational product. Investigators will report all serious adverse events (SAEs) that occur up to 30 days after the last dose of study drug to PAREXEL International Pharmacovigilance. In addition, SAEs considered by the Investigator to be related to study drug that occur >30 days after the last dose will be reported.
- f: If a subject prematurely discontinues on a blood sample collection day for PK/PD assessments (see Schedule 4), every effort should be made to collect the PK/PD sample(s) according to schedule. If a subject discontinues on a day when PK/PD assessments are not scheduled, a single PK/PD blood sample should be collected with sampling time recorded in the CRF.

Schedule 4: Blood Sample Collection Time Points for PK/PD Assessments

| C1 INH Antigen (Protein Volume), Functional C1 INH Activity (Potency), | T | REATMENT PERIO | D (BY STUDY WEE | K) | Early |
|---|----------------|----------------|-----------------|-----------------|--------------------------|
| and Complement C4 | Week 1 | Week 2 | Week 3 | Week 12 | Discontinuation Visit |
| Sample Time | Dosing Visit 1 | Dosing Visit 3 | Dosing Visit 5 | Dosing Visit 24 | [If Applicable] |
| Prior to infusion of study drug | X ^a | X | X | X | |
| 0.5 hour after start of infusion | X ^b | | | X ^b | |
| 1 hour after start of infusion | X ^c | | | X ^c | |
| 2 hours after start of infusion | X ^c | | | X ^c | X g |

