Throughout the trial, a study diary will be used by subjects (or caregivers) to record specific information about any angioedema attack symptoms and details on the self-administration of investigational product (see Section 6.11). Because of the potential to precipitate an angioedema attack, subjects will be requested to postpone elective medical procedures (eg, dental work) and avoid other known attack triggers while participating in the study (see Section 6.10).

Safety will be assessed by monitoring adverse events and changes in physical examinations, vital signs, and clinical safety laboratory testing. In addition, subjects will be monitored for the development of antibodies to C1 INH. If clinically indicated, study personnel may perform examinations to actively monitor subjects for possible venous thromboembolism or other thrombotic or thromboembolic (T/TE) events. Stopping rules are provided in Section 5.5.

Protocol 0624-209 with Amendments 1, 2, 3, 4, and CINRYZE (C1 inhibitor [human])

In this study, angioedema attacks will not be reported as adverse events unless the attack meets the definition of a serious adverse event (see Section 9.1.4).

Adverse events will be recorded from the time the informed consent is signed through 7 days after the last dose of investigational product. This includes events occurring during the screening phase of the study, regardless of whether or not the investigational product is administered. In addition, the investigator will report all SAEs that occur through 30 days after the last dose of investigational product to PAREXEL International Pharmacovigilance and the respective Independent Reviewing Authority according to local reporting requirements.

Post-treatment follow-up visits will be performed 1 week (± 1 day) and 1 month (30 ± 2 days) after the last dose of study drug. If a subject prematurely discontinues investigational product, regardless of the reason, the Early Discontinuation Visit procedures listed in Schedule 3 are to be performed as completely as possible. Whenever possible, all discontinued subjects should also complete the 1-Week and 1-Month Post-treatment Follow-up visits.

The schedules of study procedures are provided as follows:

- Schedule 1: Clinical Study Assessments Screening and Treatment Period;
- Schedule 2: Investigational Product and Self-administration Training;

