4.2 Exclusion Criteria

To be eligible for this protocol, a subject must not:

- 1. Have a history of hypercoagulability (abnormal blood clotting).
- 2. Have a diagnosis of acquired angioedema or be known to have C1 INH antibodies.
- 3. Have a history of allergic reaction to C1 INH products, including CINRYZE (or any of the components of CINRYZE) or other blood products.
- 4. Have received C1 INH therapy or any blood products within 3 days before the first dose of study drug.
- 5. Have had signs or symptoms of an angioedema attack within 2 days before the first dose of study drug.
- 6. Have any change (start, stop, or change in dose) in androgen therapy (eg, danazol, oxandrolone, stanozolol, testosterone), tranexamic acid, epsilon-aminocaproic acid (EACA), or other antifibrinolytics within 14 days before the first dose of study drug.
- 7. If female, have started taking or changed the dose of any hormonal contraceptive regimen or hormone replacement therapy (eg, estrogen/progestin containing products) within 2 months before the first dose of study drug.
- 8. Be pregnant or breastfeeding.
- 9. Have received an investigational drug other than those required for prevention or treatment of angioedema attacks within 30 days before the first dose of study drug.
- 10. Have, as determined by the Investigator and/or the Sponsor's Medical Monitor, any surgical or medical condition that could interfere with the administration of study drug or interpretation of study results.

Protocol 0624-209 with Amendments 1, 2, 3, 4, and 5 CINRYZE (C1 inhibitor [human])

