6.8 Sample Collection for Pharmacokinetic, Pharmacodynamic, and C1 INH Antibody Analyses

Subjects will have blood samples collected for the determination of plasma concentrations of C1 INH antigen (protein volume), functional C1 INH activity (potency), complement C4, and C1q at the time points specified in Schedule 4. In addition, blood samples will be collected at Visits 1 (baseline), 8, 16, and 24 and 1 month (30 ± 2 days) after the last dose of study drug for C1 INH antibody analyses (see Schedule 1 and Schedule 3).

The actual date and time of each sample collection will be recorded. Plasma samples for the determination of C1 INH antigen (protein volume), functional C1 INH activity (potency), complement C4, and C1q concentrations and C1 INH antibodies will be analyzed using fully validated methodology. Details on the processing of blood samples for PK/PD and immunogenicity assessments will be provided in a separate study manual.

NOTE: If a subject presents to the site with a breakthrough angioedema attack, every effort should be made to obtain a PK blood sample before treatment. In addition, if the subject receives CINRYZE for treatment of the attack, every effort should be made to obtain a 1-hour post-treatment sample; if a second dose of CINRYZE is administered, an additional 1-hour post-treatment sample should be obtained if possible. These samples will be collected as an unscheduled visit and analyzed for C1 INH antigen (protein volume) and functional C1 INH activity (potency). Additional blood samples for PK/PD and C1 INH antibody assessments may be collected during the study if clinically indicated.

Selected samples may be analyzed to investigate incurred sample reproducibility (ISR) of the bioanalytical methods and/or incurred sample stability (ISS). These analyses are only to investigate the reproducibility of the bioanalytical methods used to determine concentrations of

C1 INH antigen (protein volume) and functional C1 INH activity (potency) in study samples and/or to investigate the stability of the incurred samples. All ISR and ISS results collected will be reported in a separate table in the bioanalytical report. All samples will be disposed of at the conclusion of the study. Details of disposal will be documented and maintained with the study file at the analytical laboratory.

Selected samples may be retained to investigate immunogenicity to C1 INH.

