#### 4.3. SAFETY ASSESSMENTS

The following will be assessed:

- Adverse events (including treatment-emergent adverse events).
- Summary statistics and changes from baseline to post-baseline for laboratory testing, vital signs, and, if applicable, any electrocardiogram (ECG) findings will be presented.
- Results of C1-INH antibody testing will be reported for individual subjects and summarized as appropriate.

\\SW20RND01\VistaTempDir\Temp28232\Shire\_0624\_209\_SAP\_v1 0.docx Document:

Template No: CS\_TP\_BS016 Revision 4 Reference: CS\_WI\_BS005

Version Number:

Version Date:

1.0

21Jul2017

Effective Date: 01Apr2016

Author:

Shire
PROTOCOL: 0624-209
Page 12 of 35

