# 5.9. IMMUNOGENICITY (C1-INH ANTIBODY) AND PHARMACOKINETIC CONCENTRATIONS AND PHARMACODYNAMICS LEVELS

The concentrations of C1-INH antigen (protein volume), functional C1-INH activity (potency), and complement C4 and C1q for individual subjects will be determined using fully validated bioanalytical methods, and will be listed and summarized using descriptive statistics at each time point. C1q concentrations will be assessed at baseline only (ie, pre-infusion, Dosing Visit 1).

The Antibody results will be listed and summarized using descriptive statistics at each nominal time point.

\\SW20RND01\VistaTempDir\Temp28232\Shire 0624 209 SAP v1 0.docx Document: PPD Version Number: Author:

Version Date: 21Jul2017

Template No: CS\_TP\_BS016 Revision 4

PROTOCOL: 0624-209 Page 26 of 35

1.0

21Jul2017

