## 9. APPENDICES

# 9.1. APPENDIX I – LIST OF STATISTICAL OUTPUTS

#### 9.1.1. LIST OF PLANNED TABLES

Table 14.1.1.1 Subject Disposition (All Screened Subjects)

Table 14.1.2.1 Protocol Deviations (Intent-to-Treat Safety Analysis Set)

Table 14.1.4.1 Demographic and Baseline Characteristics (Intent-to-Treat Safety Analysis Set)

Table 14.1.4.3.1 Summary of HAE History (Intent-to-Treat Safety Analysis Set)

Table 14.1.4.3.2 Summary of Medical History (Intent-to-Treat Safety Analysis Set)

Table 14.1.4.4 Prior Medications and Therapy (Intent-to-Treat Safety Analysis Set)

Table 14.1.4.5 Concomitant Medications and Therapy (Intent-to-Treat Safety Analysis Set)

Table 14.2.1.1 Summary of Angioedema Attacks during Treatment Period (Full Analysis Set)

Table 14.2.1.2.1 Sensitivity Analysis Completed Schedules - Summary of Angioedema Attacks during Treatment Period (Full Analysis Set)

Table 14.2.1.2.2 Sensitivity Analysis Treatment Compliance - Summary of Angioedema Attacks during Treatment Period (Full Analysis Set)

Table 14.2.1.3 Analysis of Clinical Responder Rate – Achieving at least 50%, 70% or 90% Reduction Relative to Historical Data in NNA (Full Analysis Set)

Table 14.2.2.1.1 Summary of Breakthrough Angioedema Attacks Treated By CINRYZE (Full Analysis Set)

Table 14.2.2.1.2 Summary of Breakthrough Angioedema Attacks Treated By Non-CINRYZE C1-INH (Full Analysis Set)

Table 14.2.2.1.3 Summary of Other Breakthrough Angioedema Attacks Not Treated with C1-INH (Full Analysis Set)

Table 14.2.2.1.4 Summary and Change from Baseline on AE-QoL (Full Analysis Set)

Table 14.2.3.1 C1-INH Antigen, Functional C1-INH activity, Complement C4 and C1q (Intent-to-Treat Safety Analysis Set)

Table 14.2.3.2 Antibody Results (Intent-to-Treat Safety Analysis Set)

Table 14.3.1.1 Overall Treatment-emergent Adverse Events (TEAEs) (Intent-to-Treat Safety Analysis Set)

Table 14.3.1.2.1 Treatment-emergent Adverse Events by System Organ Class and Preferred Term (Intent-to-Treat Safety Analysis Set)

Document: \\SW20RND01\\VistaTempDir\Temp28232\\Shire\_0624\_209\_SAP\_v1 0.docx

Version Date: 21Jul2017

Version Number:

1.0

Template No: CS TP BS016 Revision 4 Reference: CS WI BS005

Effective Date: 01Apr2016

Author:

Table 14.3.1.2.2 Serious Treatment-emergent Adverse Events by System Organ Class and Preferred Term (Intent-to-Treat Safety Analysis Set)

Table 14.3.1.3.1 Treatment-emergent Adverse Events by Preferred Term (Intent-to-Treat Safety Analysis Set)

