#### 9.1.3. LIST OF PLANNED LISTINGS

Listing 16.2.1.1 Subject Disposition (All Enrolled Subjects)

Document: \\SW20RND01\\VistaTempDir\Temp28232\\Shire\_0624\_209\_SAP\_v1 0.docx

Author: PPD Version Number: 1.0
Version Date: 21Jul2017

Template No: CS TP BS016 Revision 4 Reference: CS WI BS005

Shire
PROTOCOL: 0624-209
Page 31 of 35

Listing 16.2.1.2 Subjects Who Terminated from the Study (All Enrolled Subjects)

Listing 16.2.2.1 Deviations from Inclusion/Exclusion Criteria (All Enrolled Subjects)

Listing 16.2.2.2 Protocol Deviations (All Enrolled Subjects)

Listing 16.2.4.1 Subject Demographic and Baseline Characteristics (Intent-to-Treat Safety Analysis Set)

Listing 16.2.4.3.1 Hereditary Angioedema (HAE) History (Intent-to-Treat Safety Analysis Set)

Listing 16.2.4.3.2 Hereditary Angioedema (HAE) History Detail (Intent-to-Treat Safety Analysis Set)

Listing 16.2.4.3.3 Medical History (Intent-to-Treat Safety Analysis Set)

Listing 16.2.4.4.1 Prior and Concomitant Medications (Intent-to-Treat Safety Analysis Set)

Listing 16.2.4.4.2 Concomitant Medical/Surgical Procedures (Intent-to-Treat Safety Analysis Set)

Listing 16.2.5.2.1 Study Drug Administration (Intent-to-Treat Safety Analysis Set)

Listing 16.2.5.2.2 Study Drug Exposure (Intent-to-Treat Safety Analysis Set)

Listing 16.2.5.3 C1-INH Antigen, Functional C1-INH activity, Complement C4 and C1q (Intent-to-Treat Safety Analysis Set)

Listing 16.2.5.4 Antibody Results (Intent-to-Treat Safety Analysis Set)

Listing 16.2.6.1 Subject Data of Angioedema Attack (Intent-to-Treat Safety Analysis Set)

Listing 16.2.6.2 Subject Data of Breakthrough Attack (Intent-to-Treat Safety Analysis Set)

Listing 16.2.6.3 Investigator Assessment of Breakthrough Attack (Intent-to-Treat Safety Analysis Set)

Listing 16.2.6.4 Self-administration Survey (Intent-to-Treat Safety Analysis Set)

Listing 16.2.6.5 Treatment Compliance (Intent-to-Treat Safety Analysis Set)

Listing 16.2.7.1 Adverse Events (Intent-to-Treat Safety Analysis Set)

Listing 16.2.7.2 Serious Adverse Events (Intent-to-Treat Safety Analysis Set)

Listing 16.2.8.1.2 Clinical Laboratory Test Results (Intent-to-Treat Safety Analysis Set)

Listing 16.2.8.1.3 Subjects with Potentially Clinically Important Laboratory Test Results (Intent-to-Treat Safety Analysis Set)

Listing 16.2.8.2.1 Vital Signs (Intent-to-Treat Safety Analysis Set)

Listing 16.2.8.2.2 Subjects with Potentially Clinically Important Vital Signs (Intent-to-Treat Safety Analysis Set)

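### The antibody summary in SAP 5.9 gives prevalence at each visit, not the number of subjects who developed C1 INH antibodies on treatment

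*SAP*

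**What the plan says.** Protocol section 3 (and the synopsis) states the aim: "subjects will be monitored for the development of antibodies to C1 INH". Protocol 6.8 sets the sampling: "blood samples will be collected at Visits 1 (baseline), 8, 16, and 24 and 1 month" after the last dose. Schedule 1 places the Visit 1 sample before dosing, and Schedule 3 adds a sample at an Early Discontinuation Visit. Section 6.8 also allows extra antibody samples when clinically indicated.

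On eligibility, exclusion criterion 2 in Protocol 4.2 reads: "Have a diagnosis of acquired angioedema or be known to have C1 INH antibodies". Schedule 1 has no antibody test at screening. Exclusion criterion 4 bars C1 INH therapy only in the 3 days before the first dose.

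On analysis, SAP 4.3 repeats the general statement of Protocol 7.4: "Results of C1-INH antibody testing will be reported for individual subjects and summarized as appropriate". SAP 5.9 makes it specific: "The Antibody results will be listed and summarized using descriptive statistics at each nominal time point". The outputs are one table (14.2.3.2) and one listing (16.2.5.4), both on the ITT-S set. SAP 5.1 keeps data from unscheduled visits out of the analysis unless otherwise specified and shows them in listings only. Section 5.9 specifies nothing different.

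**The concern.** Development of an antibody is a change within a subject: negative before treatment, positive at some time after it. A proportion positive at each visit is a different quantity, and it departs from the first in three ways.

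- A subject with an unrecognised antibody can be enrolled, because only known carriers are excluded. If the antibody persists, that subject is positive in every later row without having developed anything on study.
- Subjects who convert at different visits appear as separate small fractions, and no row adds them up.
- A conversion found only in a clinically indicated extra sample reaches the listing but no summary.

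The SAP already accounts for baseline elsewhere in the safety data: adverse events have a treatment-emergent definition (5.8.1), and haematology, chemistry and coagulation have change and shift from baseline (5.8.2). Antibodies have neither. Without a definition fixed in advance, whoever writes the report must choose after seeing the data which samples and which denominator to use for the number who developed antibodies.

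**Working it through.** **Is there a figure to reproduce?** No. The documents give no antibody rate, and the minimum of 6 completers (Protocol 7.1, SAP 3.2) has no statistical derivation. The check is therefore a counting exercise with assumed patterns.

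**Inputs.** n = 6 subjects, the planned minimum of completers. There are five scheduled sampling times (Visits 1, 8, 16, 24 and 1 month), of which four are post-baseline.

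**Formulas.**
- By-visit figure: subjects positive at that visit / subjects tested at that visit.
- Treatment-emergent figure: subjects negative at Visit 1 and positive at any later sample / subjects negative at Visit 1 with at least one later result.

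**Results** (all patterns assumed, no missing samples):

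| Pattern | Visit 1 | Visit 8 | Visit 16 | Visit 24 | 1 month | Treatment-emergent |
|---|---|---|---|---|---|---|
| A. One subject positive throughout, nobody converts | 1/6 | 1/6 | 1/6 | 1/6 | 1/6 | 0/5 (0%) |
| B. Three transient conversions, one each at Visits 8, 16 and 24 | 0/6 | 1/6 | 1/6 | 1/6 | 0/6 | 3/6 (50.0%) |
| C. One subject positive throughout, plus four transient conversions, one at each post-baseline time | 1/6 | 2/6 | 2/6 | 2/6 | 2/6 | 4/5 (80.0%) |

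In A the table shows 1/6 = 16.7% at every post-baseline time although nobody converted. In B no visit exceeds 16.7% although half the subjects converted. With no baseline positives and k subjects each converting once at a different visit, the highest row stays at 1/6, while the cumulative figure is 2/6 (33.3%), 3/6 (50.0%) or 4/6 (66.7%) for k = 2, 3 or 4.

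**Can the rows be turned back into a count?** Not from the rows alone. The rows in B (0, 1, 1, 1, 0) fit one subject positive at Visits 8, 16 and 24 (1/6), two subjects sharing those visits (2/6), or three different subjects (3/6). The number of converters lies anywhere between the largest row, 1, and the sum of the rows, 1 + 1 + 1 = 3. Only subject-level data settle it.

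**Are baseline positives possible?** Yes, though their frequency is not stated. Criterion 2 depends on prior knowledge, no screening test is scheduled, and earlier C1 INH use is allowed. Subjects must average at least one attack a month before entry (Protocol 4.1), and the only product that Protocol section 1 names as approved in Japan for HAE is itself a C1 inactivator for acute attacks. Prior exposure is therefore realistic.

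**The case against.** The strongest reply is that the information is already there. SAP 5.9 plans a listing as well as a summary, and SAP 4.3 commits to reporting individual subjects. At the minimum of 6 completers with five scheduled samples each, there are 6 × 5 = 30 results, and anyone can read conversions from them. Visit 1 is itself a row, so a baseline positive is visible in the table. The later rows are correct as prevalence, and the SAP nowhere calls them incidence. The trial is descriptive, and no stopping rule in Protocol 5.5 uses an antibody rate. All of this stands, and it limits the weight of the point. It does not supply the missing count.

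A reader might also infer three stronger things that the documents do not support.

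- *That the table misstates the antibody rate.* It does so only if prevalence is read as incidence. The broad wording of SAP 4.3 would also permit a cumulative count, although it does not specify one, and no table shell is shown.
- *That an early leaver's sample drops out of the table.* No text removes it. Early discontinuation is a protocol-defined visit, and the listing-only rule in SAP 5.1 concerns unscheduled visits. Schedule 3 also asks discontinued subjects to attend the 1-Month visit where possible, which has its own antibody sample.
- *That a rise from a positive baseline can be counted from the planned data.* This needs a titer or level, and the documents do not describe the assay output.

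**Conclusion.** The point holds as a minor one. The stated summary answers how many subjects are positive at each visit, while the protocol asks how many develop antibodies. The SAP defines no baseline-negative denominator, no treatment-emergent positive and no ever-positive count, and it leaves unscheduled antibody samples out of every summary. The information is unsummarized, not lost.

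The gap between the two figures depends entirely on patterns that the documents do not predict. In the examples it runs from 16.7% shown against 0% emergent to 16.7% shown against 66.7% emergent. These rest on 6 subjects and assumed patterns, and they illustrate arithmetic, not expected bias. If no subject is ever positive, both summaries show zero and the added row only states it. The point concerns analysis and tabulation. It touches no dose, schedule, rescue or stopping rule.

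**What to change.** In SAP 5.9 and Table 14.2.3.2:

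1. Define treatment-emergent antibody as negative at Visit 1 and positive at any later sample, whether scheduled, early discontinuation, 1-Month or unscheduled. State that this is an exception to the unscheduled-visit rule in SAP 5.1.
2. Report n/N (%), with N the subjects who have a negative baseline and at least one post-baseline result.
3. Show baseline-positive subjects on a separate row. Count a rise from a positive baseline only if the assay reports a titer or level.
4. Keep the by-visit rows and Listing 16.2.5.4 as they are.

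The cost is a definition and one or two rows in a planned table, from samples already in the protocol. The only conditional part is the rise from a positive baseline, which depends on the assay output.

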# 6. CHANGES IN THE CONDUCT OF THE STUDY OR PLANNED ANALYSES

#### 6.1. CHANGES IN THE CONDUCT OF THE STUDY

No changes in the conduct of the study.

#### 6.2. CHANGES FROM THE ANALYSES PLANNED IN THE PROTOCOL

Due to insufficient data collection, the analysis of clinical relief has not been conducted as planned.

\\SW20RND01\\VistaTempDir\Temp28232\\Shire\_0624\_209\_SAP\_v1 0.docx PPD Version Number: Document: Author:

Version Date: Reference: CS\_WI\_BS005

Template No: CS\_TP\_BS016 Revision 4

Effective Date: 01Apr2016

Copyright © 2009, 2010, 2012, 2016 Quintiles Transnational Corp. All rights reserved.

Shire
PROTOCOL: 0624-209
Page 27 of 35

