In addition to the subject's self-assessment, the Investigator should assess and record the overall severity every 15 minutes for up to 4 hours post-infusion if the subject seeks treatment at the site.

NOTE: If a subject has adequately responded to treatment with CINRYZE, the subject may omit further assessments up to 4 hours post-infusion (and if applicable, be discharged from the investigational site) provided that overall attack severity has been assessed for at least 1 hour.

Subject diary data will be used by study personnel to record the onset date and time of the breakthrough attack, as well as the date and time of onset of symptom improvement and Complete Resolution (defined in Section 7.6.2) in the CRF.

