7.6.2 Treatment of Breakthrough Angioedema Attacks

The following efficacy endpoints for treatment of breakthrough angioedema attacks will be assessed by CINRYZE-treated attack number:

- The number of subjects who achieve Clinical Relief. Clinical Relief is defined as a sustained reduction from pre-infusion in the attack severity within 4 hours after initiation of treatment with CINRYZE.
- Time to onset of Clinical Relief.
- The number of subjects who achieve Complete Resolution. Complete Resolution is defined as the cessation of all symptoms of the breakthrough angioedema attack.
- Time to Complete Resolution.

Other analyses may be performed to establish context of the efficacy results from this study with previous Phase 3 CINRYZE studies.

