#### 5.7.2. TREATMENT OF BREAKTHROUGH ANGIOEDEMA ATTACKS

A breakthrough attack is defined as an angioedema attack that occurs during long-term prevention therapy with CINRYZE® (i.e, between first study drug and last study drug dose).

The following efficacy endpoints for treatment of breakthrough angioedema attacks will be assessed by CINRYZE® treated attacks, non-CINRYZE® C1-INH treated attacks and all other attacks (including any medications other than C1-INH and untreated attacks):

- The number of subjects with breakthrough angioedema attacks.
- The number of subjects with 1, 2, 3 or more angioedema attacks.
- The number of subjects who achieve initial improvement and Complete Resolution.
- Time to initial improvement and time to Complete Resolution.

Additional analysis for breakthrough angioedema attacks treated with CINRYZE® will also be presented for:

- The number of subjects with breakthrough angioedema attacks.
- The number of subjects with 1, 2, 3 or more angioedema attacks.
- Time from onset of attack to time treated by CINRYZE.
- The number of subjects who achieve initial improvement and Complete Resolution. Complete Resolution is defined as the cessation of all symptoms of the breakthrough angioedema attack since onset of attack.
- Time from the start of study drug administration, CINRYZE°, for the particular attack to the time of initial improvement and time to Complete Resolution.

\\SW20RND01\\VistaTempDir\Temp28232\Shire\_0624\_209\_SAP\_v1 0.docx Document: Version Number:

Version Date: 21Jul2017

Template No: CS\_TP\_BS016 Revision 4

Effective Date: 01Apr2016

Author:

Copyright © 2009, 2010, 2012, 2016 Quintiles Transnational Corp. All rights reserved.

The contents of this document are confidential and proprietary to Quintiles Transnational Corp. Unauthorized use, disclosure or reproduction is strictly prohibited.

Shire
PROTOCOL: 0624-209
Page 18 of 35

Derivations will be constructed as follow:

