#### **Complete Resolution**

Complete Resolution is defined as the cessation of all symptoms of the breakthrough angioedema attack since onset of attack.

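### With Clinical Relief dropped, breakthrough attacks have no time-bounded response measure, and the new count of initial improvement is undefined, open-ended and not listed as a change

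*SAP*

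**What the plan says.** Protocol 7.6.2 names four endpoints for CINRYZE-treated breakthrough attacks: the number of subjects with Clinical Relief, time to its onset, the number with Complete Resolution, and time to Complete Resolution. Clinical Relief is a "sustained reduction from pre-infusion in the attack severity within 4 hours after initiation of treatment with CINRYZE". Complete Resolution has no window: "Complete Resolution is defined as the cessation of all symptoms of the breakthrough angioedema attack".

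SAP 6.2 has one entry: "Due to insufficient data collection, the analysis of clinical relief has not been conducted as planned". It does not say which data were lacking and mentions no substitute.

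SAP 4.2.2 and 5.7.2 list "The number of subjects who achieve initial improvement and Complete Resolution" and "Time to initial improvement and time to Complete Resolution". These are tabulated for three groups: attacks treated with CINRYZE, attacks treated with another C1-INH product, and all others, including untreated attacks. For CINRYZE-treated attacks, 5.7.2 adds the time from the start of CINRYZE to each event. The derivations define only Complete Resolution and the time to it. Initial improvement has no stated scale, size of change, duration, assessor or window.

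SAP 5.1 and 5.7.2 plan Kaplan-Meier medians with 95% confidence intervals, and plots of time from CINRYZE to initial improvement and to Complete Resolution. The time-to-event analysis uses the first qualifying attack per subject.

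Protocol 6.12.2 has study staff use diary data to enter the onset of the attack in the CRF, "as well as the date and time of onset of symptom improvement and Complete Resolution".

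**The concern.** Clinical Relief was the only response measure that asked whether subjects improved soon after the drug was given. What is left in the responder counts is whether they ever improved or ever resolved. The study has no control arm, needs only 6 completers, and studies attacks that come and go. A statement that all treated subjects improved could therefore be read as evidence of efficacy when it may only show that attacks end.

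The missing definition adds to this. A reader cannot tell what change counts as initial improvement, and nothing in SAP 6.2 says that it is a new endpoint.

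**Working it through.** **No figure to reproduce.** Neither document states a response rate, power or effect size for the breakthrough endpoints. The check is a comparison of texts followed by a conditional illustration.

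**Step 1: protocol against SAP.**

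| Measure | Protocol 7.6.2 | SAP 4.2.2, 5.7.2, 6.2 |
|---|---|---|
| Clinical Relief within 4 h, sustained | count and time to onset | dropped |
| Initial improvement | not an endpoint | count and time; no definition or window |
| Complete Resolution | count and time; no window | count and time; no window |

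Only initial improvement is new, and only Clinical Relief had a time bound.

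**Step 2: do the documents expect attacks to end without CINRYZE?**
- A new attack needs a full symptom-free calendar day before it (Protocol 6.12). Any attack followed by another counted attack has therefore ended, whatever was given.
- SAP 5.7.1 measures duration from onset to complete resolution, and historical duration is recorded in days (Protocol 6.1).
- The same counts are planned for attacks not treated with C1-INH (SAP Table 14.2.2.1.3).

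This shows that resolution without the drug is expected, but not how often or how fast.

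**Step 3: illustration.** Assumptions, none of them from the documents:
- Time to improvement is exponential with untreated median m, so P(event by t) = 1 − 2^(−t/m).
- m is 6, 12, 24, 48 or 72 h.
- The drug doubles the hazard, so P = 1 − 2^(−2t/m). The factor 2 borrows the doubled rate of relief that Protocol 1.1.2 reports for the overseas treatment study, and treating it as a hazard ratio is a further assumption.
- 7 and 14 days stand in for no time limit.

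Example, m = 24 h and t = 4 h: untreated 1 − 2^(−4/24) = 10.9%; with drug 1 − 2^(−8/24) = 20.6%.

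| m (h) | By 4 h: untreated / drug | By 7 days: untreated / drug | By 14 days: untreated / drug |
|---|---|---|---|
| 6 | 37.0% / 60.3% | 100% / 100% | 100% / 100% |
| 12 | 20.6% / 37.0% | 100% / 100% | 100% / 100% |
| 24 | 10.9% / 20.6% | 99.2% / 100% | 100% / 100% |
| 48 | 5.6% / 10.9% | 91.2% / 99.2% | 99.2% / 100% |
| 72 | 3.8% / 7.4% | 80.2% / 96.1% | 96.1% / 99.8% |

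At 4 h the drug-to-untreated ratio is 1.6 to 2.0 throughout. By 14 days the difference is at most 3.8 percentage points.

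For six untreated subjects, the chance that all six count as improved is P^6. By 14 days it is 0.79 (m = 72 h), 0.95 (48 h) and above 0.99 (24 h or less). By 7 days it is 0.27, 0.57 and at least 0.95 respectively. By 4 h it is at most 0.370^6 = 0.003.

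**Step 4: what the Kaplan-Meier analysis covers.** Time from CINRYZE to each event carries the information on speed. There are two limits:
- SAP 5.1 gives a median only if at least 50% of the Full Analysis Set had the event. Read literally, with 6 subjects in the set and 2 having a CINRYZE-treated attack, 2/6 = 33% and no median is reported. The open-ended count could still show 2 of 2.
- The derivation of time to Complete Resolution starts at attack onset, while the CINRYZE analysis and plots start at dosing.

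**The case against.** The best defence is that timing has not been lost. The SAP plans time from CINRYZE to both events with plots, and with so few subjects the share improved by 4 hours could be read off the curve. The dropped endpoint is disclosed with a reason in the section meant for it. This stands in part: speed is still described, but no 4-hour figure is tabulated, and initial improvement is neither defined nor disclosed.

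Three stronger readings might be inferred, and the documents do not support them.

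- *Both open-ended counts replaced Clinical Relief.* Complete Resolution without a window was in the protocol from the start of this comparison; compare "Complete Resolution is defined as the cessation of all symptoms of the breakthrough angioedema attack" with the SAP's "Complete Resolution is defined as the cessation of all symptoms of the breakthrough angioedema attack since onset of attack". Only initial improvement is new.
- *The counts reach 100% whatever the drug does.* No untreated rate is given. Missing times are not imputed (SAP 7.1) and the diary ends at the 1-week follow-up visit, so counts can fall short. The 7-day column shows that with long medians they need not saturate.
- *The results cannot be set beside earlier studies.* The overseas treatment result in Protocol 1.1.2 is a relative rate of beginning of unequivocal relief, with no 4-hour window stated. A time-to-onset analysis may be a fair counterpart, and Protocol 7.6.2 leaves room for other contextual analyses.

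It is also not certain that the needed times were obtained. Protocol 6.12.2 says what staff will record, and SAP 6.2 does not say what was missing. A 4-hour row must therefore report missing times. However, if the times support the planned Kaplan-Meier curve, they support this row too.

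**Conclusion.** The point holds in this form: after SAP 6.2, no time-bounded responder measure remains for breakthrough attacks. The count that enters alongside Complete Resolution has neither a definition nor a window, and is not listed as a change. The planned time-from-CINRYZE analyses soften the loss but do not remove it.

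That open-ended counts can approach 100% without a drug effect depends on attacks ending on their own. The documents imply that they do but do not quantify it. The size (96% or more by 14 days against 4% to 37% by 4 hours, untreated) rests on the assumed medians and exponential times, and is an illustration rather than an estimate for this trial. The change is worth making because it is cheap and prevents a misleading headline; it does not invalidate the descriptive analysis.

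**What to change.** In SAP 5.7.2, for the first CINRYZE-treated attack per subject, add the number and percent with initial improvement within 4 hours after the start of CINRYZE, or the Kaplan-Meier estimate at 4 hours with its 95% confidence interval. The denominator is subjects with a CINRYZE-treated attack.

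- Define initial improvement as the recorded date and time of onset of symptom improvement (Protocol 6.12.2).
- Report how many of these times are missing.
- Flag subjects who received a second dose or other treatment before improvement.
- Label the row an approximation to Clinical Relief that does not verify that the reduction was sustained.
- List initial improvement and the new row in SAP 6.2 as changes from the protocol.
- State that the open-ended counts are descriptive only.

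No new data are needed: infusion start times (Protocol 5.3) and improvement times are both meant to be in the CRF, and the SAP already plans to analyse the interval between them. The cost is one table row, a definition and a few sentences. The downside is that the row only approximates the protocol's endpoint and will probably look less favourable than the open-ended count.
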